4.1 Dose modification, interruption or discontinuation of treatment

If an adverse event is clearly associated to one of study drugs, the dose adjustment directed for that study drug will be followed; however, if the causality is not clear, then it may be necessary to adjust both study drugs. Dosing adjustments will be discussed with the sponsor. If a patient experiences a DLT then treatment with Sonidegib plus buparlisib must be stopped and the patient may be discontinued from the study. However, following resolution of the DLT to CTCAE Grade 1 or to the patient's baseline value, the patient may continue to receive study treatment with a 50% dose reduction for either sonidegib, buparlisib or both, if appropriate, at the discretion of the investigator and after discussion with the Sponsor.

If a patient requires a dose delay of > 21 days due to an sonidegib- or buparlisibrelated toxicity, then the patient must be discontinued from the study; however, if the patient is obtaining clinical benefit (ie, SD, PR, or CR), the patient may continue treatment at the same or at a reduced dose following discussion between the investigator and Novartis. All patients will be followed for AEs and SAEs for 30 days following the last dose of sonidegib and/or buparlisib. If the administration of study treatment was interrupted for reasons other than toxicity, then treatment with Sonidegib and buparlisib may be resumed at the same dose.

Patients who experience hematologic, renal, hepatic, or muscle toxicities should receive follow up and dosing modifications for sonidegib as per Table 9 and 10 below. Specific instructions for follow-up and dosing modifications for sonidegib are described in detail in Table 9. Patients who experience muscle toxicity, regardless of whether the toxicity meets the criteria described for a DLT, should be receive follow-up and dosing modifications specified in Table 9 below.

Table 9. Recommended dose modifications and dose delays for suspected sonidegib** treatment-related toxicities	
Worst toxicity CTCAE grade* (value)	During a cycle of therapy
Не	ematologic
Neutropenia (ANC)	
Worst toxicity CTCAE grade* (value)	During a cycle of therapy
Grade 1 (ANC < LLN - 1500/mm ³)	Maintain dose level
Grade 2 (ANC < 1500 - 1000/mm ³)	Maintain dose level
Grade 3 or 4 (ANC < 1000 - 500/mm ³ or < 500/mm ³)	Omit dose until resolved to ≤ Grade 1, then: • If resolved in ≤ 7 days, implement 50% dose reduction • If resolved in > 7 days, discontinue drug • If a Grade 4 event, consider hospitalization if appropriate
Thrombocytopenia (PLT)	
Grade 1 (PLT < LLN - 75,000/mm ³)	Maintain dose level
Grade 2 (PLT < 75,000 - 50,000/mm ³)	Maintain dose level
Grade 3 or 4 (PLT < 50,000 - 25,000/mm ³ or < 25,000/mm ³)	Omit dose until resolved to ≤ Grade 1, then: •• If resolved in ≤ 7 days, implement 50% dose reduction •• If resolved in > 7 days, discontinue drug •• If a Grade 4 event, consider hospitalization if appropriate

Febrile Neutropenia	
Grade 3 (ANC $< 1.0 \times 10^9$ /L, fever \ge	Omit dose until resolved, then implement 50% dose
38.5°C)	reduction
Grade 4	Consider hospitalization
Life-threatening consequences; urgent intervention indicated	Discontinue drug

Table 9. Recommended dose modifications and dose delays for suspected sonidegib** treatment-related toxicities	
Worst toxicity CTCAE grade* (value)	During a cycle of therapy
M	uscle Toxicity
Elevated crea	atinine phosphokinase (CK)
Asymptomatic (no new-onset muscle pain/spasm or worsening of pre-existing muscle pain/spasm) CTCAE Grade 1 or 2 CK elevation	 ♦♦ For CTCAE Grade 1 CK elevation, continue treatment on same dose and continue monitoring as per schedule of assessments ♦♦ For CTCAE Grade 2 CK elevation, continue on same dose level of sonidegib. CK should be measured weekly until resolution to ≤ Grade 1.
Symptomatic (new-onset or worsening of pre-existing muscle pain/spasm) with CTCAE Grade 1 or 2 CK elevation	 ♦♦ For CTCAE Grade 1 CK with muscle pain/spasm ≥ CTCAE Grade 1, continue treatment at same dose and measure CK weekly until CK returns to normal or baseline value or muscle pain/spasm resolves ♦♦ For CTCAE Grade 2 CK with muscle pain/spasm ≥ CTCAE Grade 1, continue treatment at same dose level of sonidegib. CK should be measured weekly until CK is ≤ CTCAE Grade 1
CTCAE Grade 3 or 4 CK elevation (with or without muscle pain/spasm)	 ♦♦ Omit sonidegib dose, check blood myoglobin and monitor renal function. Measure CK weekly until resolution to Grade ≤ 1 ♦♦ Consider performing electromyography, MRI scan of symptomatic muscle group(s) and muscle biopsy ♦♦ If renal function is not impaired and resolution to ≤ CTCAE Grade 1 occurs within 21 days, consider resuming treatment at a reduced dose; CK should be measured weekly for 2 months after readministration of sonidegib ♦♦ Patients who experience renal impairment (serum

creatinine > 2x ULN) should be permanently
discontinued from the study
◆◆ If a Grade 4 event, consider hospitalization if
appropriate

Table 9. Recommended dose modifications and dose delays for suspected sonidegib** treatment-related toxicities	
Worst toxicity CTCAE grade* (value)	
Muscle pain/spasm (new onset or worsening of preexisting muscle pain/spasm)	 ♦♦ For CTCAE Grade 1 muscle pain/spasm, continue treatment on the same dose and planned assessments ♦♦ For CTCAE ≥ Grade 2 muscle pain/spasm, measure CK weekly until muscle pain resolves to ≤ Grade 1. If CK is elevated, follow guidance for CK elevation as described above. Continue treatment with sonidegib ♦♦ For new-onset CTCAE Grade 3 muscle pain/spasm, interrupt sonidegib. Collect blood sample for CK measurement at the time of dose interruption. Provide symptomatic treatment. Measure CK weekly until the muscle pain/spasm resolves to ≤ Grade 1 and resume therapy at a reduced dose. Measure CK weekly for 2 months after re-administration.
	Renal
	Serum creatinine
Serum creatinine <1.5 x ULN	Maintain dose level
Serum creatinine 1.5-3 x ULN	Omit dose until resolved to ≤ Grade 1, then: ◆ If resolved in ≤ 7 days, then maintain dose level • If resolved in > 7 days, then implement 50% dose reduction (consider checking serum CK, if not already done)
Grade 3 Serum creatinine > 3.0 - 6.0 x ULN	Omit dose until resolved to ≤ Grade 1 then implement 50% dose reduction
Grade 4 Serum creatinine > 6.0 x ULN	Omit dose and discontinue study drug. Consider hospitalization if appropriate
	Hepatic
	Bilirubin
Total bilirubin <1.5 x ULN	Maintain dose level

Total bilirubin 1.5-3 x ULN	Omit dose until resolved to ≤ Grade 1, then: ♦ If resolved in ≤ 7 days, then maintain dose level ♦ If resolved in > 7 days, then implement 50% dose reduction
Grade 3 Total bilirubin > 3.0 - 10.0 x ULN	Omit dose until resolved to ≤ Grade 1, then implement 50% dose reduction
Grade 4 Total bilirubin > 10.0 x ULN	Discontinue study drug. Consider if hospitalization is appropriate.

Table 9. Recommended dose modifications and dose delays for suspected sonidegib** treatment-related toxicities	
Worst toxicity CTCAE grade*(value)	During a cycle of therapy
	AST or ALT
Grade 1 (> ULN - 3.0 x ULN)	Maintain dose level
Grade 2 (> 3.0 - 5.0 x ULN)	Maintain dose level
Grade 3 (> 5.0 - 20.0 x ULN)	Omit dose until resolved to ≤ Grade 1 or baseline then: •• If resolved in ≤ 7 days, then maintain dose level •• If resolved in > 7 days, then implement 50% dose reduction
Grade 4 (> 20.0 x ULN)	Omit dose until resolved to ≤ Grade 1 or baseline, then implement 50% dose reduction. Consider if hospitalization is appropriate
	Cardiac
Cardiac - prolonged QTc interval Grade 3 (QTcF > 500 msec or >60 ms from baseline on at least 2 separate ECGs taken within 1 hour)	First Occurrence: ◆ Omit dose ◆ Perform an analysis of serum potassium and magnesium, and if below lower limit of normal, correct with supplements to within normal limits. Concomitant medication usage must be reviewed. ◆ Perform a repeat ECG within one hour of the first QTcF of > 500 ms ◆ If QTcF remains > 500 ms, repeat ECG as clinically indicated but at least once a day until the QTcF returns to < 480 ms. ◆ Once QTcF prolongation has resolved, study treatment may be restarted with a 50% dose reduction Second Occurrence: ◆ discontinue patient from study drug

Cardiac - prolonged QTc interval	Discontinue patient from study drug
Grade 4	

Table 9. Recommended dose modifications and dose delays for suspected sonidegib** treatment-related toxicities	
Worst toxicity CTCAE grade* (value)	During a cycle of therapy
Otl	her Cardiac Events
Grade 1	Maintain dose level
Grade 2	Implement 50% dose reduction of buparlisib
Grade 3	Omit dose and discontinue study drug
Grade 4	Omit dose and discontinue study drug. Consider if hospitalization if appropriate
Oth	er adverse events**
Grade 1	Maintain dose level
Grade 2	Implement 50% dose reduction
Grade 3	Omit dose and discontinue study drug
Grade 4	Omit dose and discontinue study drug

Grade 3	Omit dose and discontinue study drug
Grade 4	Omit dose and discontinue study drug
	Consider if hospitalization if appropriate
111 1 110 1 1 1 1 1	i di

All dose modifications should be based on the worst preceding toxicity.

If the dose-limiting toxicity recurs in a patient following dose reduction, then further therapy with sonidegib will not be continued.

If a patient requires a dose interruption of > 21 days from the intended day of the next scheduled dose because of a sonidegib-related toxicity, then the patient must be discontinued from the study.

*Common Toxicity Criteria for Adverse Events (CTCAE Version 4.0).

** If the investigator deems that a recommended dose reduction or the recommendation to maintain the same dose level is not in the best interest of the patient, this decision may be discussed with Novartis on a case-by-case basis.

Criteria for follow-up and dosing modifications for buparlisib are described in detail in Table 10.

For overlapping toxicities of sonidegib and buparlisib, specifically hematologic, renal and hepatic toxicities, BOTH sonidegib and buparlisib will be reduced or discontinued depending on toxicity grade per the guidelines listed below for each drug (Tables 9 and 10).

Table 10. Recommended dose modifications and dose delays for suspected buparlisib treatment-related toxicities		
Worst toxicity CTCAE grade* (value)	During a cycle of therapy	
	Hematologic	
]	Neutropenia (ANC)	
Grade 1 (ANC < LLN - 1500/mm ³)	Maintain dose level	
Grade 2 (ANC < 1500 - 1000/mm ³)	Maintain dose level	
Grade 3 or 4 (ANC < 1000 - 500/ mm ³ or < 500/mm ³)	 Omit dose until resolved to ≤ Grade 1, then: If resolved in ≤ 7 days, implement 50% dose reduction If resolved >7 days, discontinue drug If a Grade 4 event, consider hospitalization if appropriate 	
Thrombocytopena		
Grade 1 (PLT < LLN - 75 x 10 ⁹ /L)	Maintain dose level	
Grade 2 (PLT < 75 - 50 x 10 ⁹ /L)	Maintain dose level	

Grade 3 (PLT $< 50-25 \times 10^9/L$)	Omit dose until resolved to ≤ Grade 1, then:	
	 If resolved in ≤ 7 days, then maintain dose level If resolved in > 7 days, then implement 50% dose reduction 	
Grade 4 (PLT < 25 x 109/L)	Omit dose until resolved to ≤ Grade 1, then implement 50% dose reduction. Consider if hospitalization is appropriate	
	Renal	
	Serum creatinine	
Serum creatinine <1.5 x ULN	Maintain dose level	
Serum creatinine 1.5-3 x ULN	Omit dose until resolved to ≤ Grade 1, then: •• If resolved in ≤ 7 days, then maintain dose level •• If resolved in > 7 days, then implement 50% dose reduction (consider checking serum CK, if not already done)	
Table 10. Recommended dose modifications and dose delays for suspected buparlisib treatment-related toxicities		
Worst toxicity CTCAE grade* (value)	During a cycle of therapy	
Grade 3 Serum creatinine > 3.0 - 6.0 x ULN	Omit dose until resolved to ≤ Grade 1 then implement 50% dose reduction	
Grade 4 Serum creatinine > 6.0 x ULN	Omit dose and discontinue study drug. Consider hospitalization if appropriate	
Hepatic		
Bilirubin (*for patients with Gilbert syndrome these dose modifications apply to changes in direct bilirubin only) will be fractionated if elevated		

Total bilirubin <1.5 x ULN	Maintain dose level
T . 1177 1: 150 IV	Omit dose until resolved to \leq Grade 1, then:
Total bilirubin 1.5-3 x ULN	◆◆ If resolved in ≤ 7 days, then maintain dose level
	◆◆ If resolved in > 7 days, then implement 50% dose
	reduction
Condo 2	Ourit dans until manhand to < Conda 1 than
Grade 3	Omit dose until resolved to ≤ Grade 1, then implement 50% dose reduction
Total bilirubin > 3.0 - 10.0 x ULN	implement 30% dose reduction
Grade 4	Discontinue study medication
Total bilirubin > 10.0 x ULN	Consider if hospitalization is appropriate
	AST or ALT
Grade 1 (> ULN - 3.0 x ULN)	
	Maintain dose level
Grade 2 (> 3.0 - 5.0 x ULN)	Maintain dose level
Grade 3 (> 5.0 - 20.0 x ULN)	Omit dose until resolved to < Grade 1 or baseline then:
	♦♦ If resolved in \leq 7 days, then maintain dose level
	◆◆ If resolved in > 7 days, then implement 50% dose
	reduction
Grade 4 (> 20.0 x	Discontinue study drug
ULN)	Consider if hospitalization is appropriate
AST or	ALT and concurrent Bilirubin
AST or ALT > 3.0 x ULN and	Discontinue study drug
total bilirubin > 2.0 x ULN	

*(LFTs include albumin, ALT, AST, total bilirubin (fractionated if total bilirubin > 2.0 x ULN), alkaline phosphatase (fractionated if alkaline phosphatase is Grade 2 or higher) and GGT). Monitoring (*for patients with Gilbert Syndrome: total and direct bilirubin must be monitored, intensified monitoring applies to changes in direct bilirubin only; the monitoring includes the following LFTs: albumin, ALT, AST, total bilirubin (fractionated if total bilirubin > 2.0 x ULN), alkaline phosphatase (fractionated if alkaline phosphatase is Grade 2 or higher) and GGT).

In case of any occurrence of ALT/AST/ bilirubin* increase ≥ **Grade 2** the liver function tests must be monitored **weekly** or more frequently if clinically indicated **until resolved to** ≤ **Grade 1**

In case of any occurrence of ALT/ AST/ bilirubin* increase \geq Grade 3 the liver function tests must be monitored weekly or more frequently if clinically indicated until resolved to \leq Grade 1; hereafter the monitoring should be continued every other week or more frequently if clinically indicated until the end of treatment with study medication.

Patients who discontinued study treatment should be monitored weekly, including LFTs* or more frequently if clinically indicated **until resolved to ≤ Grade 1 or stabilization** (no CTCAE grade change over 4 weeks).

Endocrine / Metabolic Fasting Plasma Glucose (FPG) during a cycle of therapy

Maintain dose level, check FPG every week initiate or intensify medication with appropriate anti-diabetic treatment as per investigator's discretion.

Instruct patient to follow dietary guidelines according to local and/or institutional standards for management of diabetes mellitus (such as those provided by the American Diabetes Association during the study.

Consider use of oral anti-hyperglycemic therapy such as metformin blood finger stick every day and if blood glucose levels are worsening for 2 consecutive days FPG assessment is recommended.

Check FPG at least weekly for 8 weeks, then continue checking at least every 2 weeks.

First occurrence:

If signs and symptoms of hyperglycemia (e.g. mental status changes, excessive thirst, polyuria), omit buparlisib immediately and manage as per Grade 3 hyperglycemia.

If asymptomatic, maintain dose and recheck FPG within 24 hours. If grade worsens to grade 3 or 4 follow specific Grade recommendations. If grade improves to grade 1 follow Grade recommendations. If FPG remains at Grade 2, reduce study drug dose to 50% of prior dose and check FPG every week initiate or intensify medication with appropriate anti-diabetic treatment as per investigator's discretion.

Instruct patient to follow dietary guidelines according to local and/or institutional standards for management of diabetes mellitus (such as those provided by the American Diabetes Association during the study.

Consider use of oral anti-hyperglycemic therapy such as metformin blood finger stick every day and if blood glucose levels are worsening for

2 consecutive days FPG assessment is recommended. Check FPG at least weekly for 8 weeks, then continue checking at least every 2 weeks.

Second occurrence:

Discontinue study drug

Table 10. Recommended dose modifications and dose delays for suspected buparlisib treatment-related toxicities	
Worst toxicity CTCAE grade* (value)	During a cycle of therapy
_	
Grade 3 (> 250-500 mg/dL)	First Occurrence : Immediately omit buparlisib, initiate or intensify medication with appropriate

(> 13.9-27.8 mmol/L)	anti-diabetic treatment, recheck FPG within 24 hours. If Grade worsens to grade 4 then follow grade 4 recommendations. If Grade improves to grade 1 or 2 follow grade 1 or 2 guidelines. If FPG remains at Grade 3*:
	Administer intravenous hydration and intervention for electrolyte/ ketoacidosis/hyperosmolar disturbances as clinically appropriate
	Discontinue study drug Monitor FPG at least twice weekly until FPG resolves to ≤ Grade 1 Initiate or continue anti-diabetic treatment as appropriate Instruct patient to follow dietary guidelines according to local and/ or institutional standards for management of diabetes mellitus (such as those provided by the American Diabetes Association) during the study Consider use of oral anti-hyperglycemic therapy such as metformin Check FPG at least weekly for 8 weeks, then continue checking at least every 2 weeks
	For non-fasting plasma glucose >250-500 mg/dL (> 13.9 - 27.8 mmol/L) accompanied by signs/symptoms of hyperglycemia (for example, mental status changes, excessive thirst, polyuria), or presence of blood or urine ketones, omit buparlisib and following guidance for management of Grade 3 fasting plasma glucose (FPG)
	d dose modifications and dose delays parlisib** treatment-related toxicities
Worst toxicity CTCAE grade* (value)	During a cycle of therapy
	Discontinue study drug

Grade 4	Discontinue study drug
(> 500 mg/dL) (>27.8 mmol/L)	Consider hospitalization if appropriate.
	Initiate or intensify medication with appropriate anti- diabetic treatment, re-check within 24 hours, if grade
	improves then follow specific grade

	recommendations. If FPG is confirmed at Grade 4:
	Administer intravenous hydration and intervention for electrolyte/ ketoacidosis/hyperosmolar disturbances as clinically appropriate Instruct patient to follow dietary guidelines according to local and/or institutional standards for management of diabetes mellitus (such as those provided by the American Diabetes Association) during the study Consider use of oral anti-hyperglycemic therapy such as metformin. Check FPG at least weekly for 8 weeks, then continue checking at least every 2 weeks if clinically indicated
	For non-fasting plasma glucose > 500 mg/dL (> 27.8 mmol/L) accompanied by signs/symptoms of hyperglycemia (for example, mental status changes, excessive thirst, polyuria), or presence of blood or urine ketones, discontinue buparlisib and following guidance for management of Grade 4 fasting plasma glucose (FPG).
	Cardiac
Cardiac - Left Ventricular systolic dysfunction	
Grade 1 or 2 Asymptomatic, resting ejection fraction 40-50%; or 10-20% drop from baseline	Reduce buparlisib dose by 50% Repeat LVEF within 4 weeks or as clinically appropriate
Table 10. Recommended dose modifications and dose delays for suspected buparlisib** treatment-related toxicities	
Worst toxicity CTCAE grade* (value)	During a cycle of therapy
Grade 3	Discontinue buparlisib
Symptomatic, ejection fraction responsive to intervention, ejection fraction 20-39% or > 20% drop from baseline	LVEF measurement to be repeated within 4 weeks or as clinically appropriate

Grade 4	Discontinue buparlisib
Refractory or poorly controlled heart	Hospitalize if appropriate
failure due to drop in ejection fraction;	Trospitalize ii appropriate
intervention such as ventricular assist	
device, intravenous vasopressor	
support or heart transplant indicated;	
ejection fraction < 20%	
*the event is considered resolved when	the patient is asymptomatic, has a resting ejection fraction
≥40% and ≤20% decrease from baseline	2 .
Cal	rdiac – QTc prolongation
Cardiac - prolonged QTc interval ≥	Refer to Table 9 Recommended dose modifications for
Grade 3 (QTcF > 500 msec	sonidegib.
or	Ç
>60 ms from	
baseline on at least 2 separate ECGs	
taken within 1 hour)	
	Other Cardiac Events
Grade 1	Maintain dose level
Grade 1	Maintain dose ievei
Grade 2	Implement 50% dose reduction of buparlisib
Grade 3	Omit dose and discontinue study drug
T 11 10 D	1 1 1 1 1 1 1 1 1 1 1 1 1 1 1 1 1 1 1 1
Table 10. Recommended dose modifications and dose delays for	
suspected dup	parlisib treatment-related toxicities
Worst toxicity CTCAE grade* (value)	During a cycle of therapy
-	
Grade 4	Omit dose and discontinue study drug
	Consider hospitalization if appropriate

Other	
Mood alteration	
* Mood questionnaire scores should be considered when assigning the AE Grade but psychiatric consult, if required, may determine the grade	

Grade 1	Maintain dose level
Mild mood alteration (or Grade 2 anxiety if present at baseline)	Note : If question 9 (suicidal ideation) on the PHQ-9 has a positive response, or worsens in severity, the patient should be referred for psychiatric consult regardless of the total questionnaire score
Grade 2 Moderate mood alteration (for	Institute appropriate co-medication under the guidance of the psychiatrist. Maintain dose level.
Anxiety only, if worsened from baseline) and if there is no concurrent medical condition that accounts for an acute increase the PHQ score.	If the condition does not resolve to ≤ Grade 1 within 14 days despite medical treatment; then implement 50% dose reduction (continue to co-medicate) Note: If question 9 (suicidal ideation) on the PHQ-9 has a positive response, or worsens in severity, the patient should be referred for psychiatric consult regardless of the total questionnaire score
Grade 3	Discontinue study medication
Severe agitation; hospitalization not indicated	Note : If question 9 on the PHQ-9 has a positive response, or worsens in severity, the patient should be referred for psychiatric consult regardless of the total questionnaire score
Grade 4	Discontinue study medication. Consider hospitalization
Life-threatening consequences; urgent	if appropriate
intervention indicated	Note: If question 9 on the PHQ-9 has a positive response, or worsens in severity, the patient should be referred for psychiatric consult regardless of the total questionnaire score

Table 10. Recommended dose modifications and dose delays for suspected buparlisib treatment-related toxicities	
Worst toxicity	During a cycle of therapy
CTCAE grade* (value)	
Rash	
Grade 1 Macules /papules covering <10% BSA with or without symptoms (e.g. pruritus, burning)	Maintain dose level. Consider to initiate appropriate skin toxicity therapy (such as antihistamines, topical corticosteroids)

Grade 2 Macules/papules covering 10-30% BSA with or without symptoms; limiting instrumental ADLs	Reduce study drug dose to 50% of prior dose. Initiate/intensify appropriate skin toxicity therapy (such as antihistamines, topical corticosteroids)
Grade 3 Macules/papules covering >30% BSA with or without associated symptoms, limiting self-care ADLs	Discontinue study drug According to the investigators discretion, a paired skin biopsy could be obtained (from both an affected and an unaffected skin area for local histopathology assessment) if clinical appropriate
Grade 4	Discontinue buparlisib. Consider if hospitalization is appropriate According to the investigators discretion, a paired skin biopsy could be obtained (from both an affected and an unaffected skin area for local histopathology assessment) if clinical appropriate.
Table 10. Recommended dose modifications and dose delays for suspected buparlisib** treatment-related toxicities	
Worst toxicity CTCAE grade* (value)	During a cycle of therapy
Fatigue (asthenia)	

Grade 1 Fatigue relieved by rest	Maintain dose level
Grade 2	Reduce study drug dose by 50% of prior
Fatigue not relieved by rest; limiting instrumental ADL	

Grade 3	Discontinue study drug
Fatigue not relieved by rest; limiting	
self care ADL	
Grade 4	Discontinue buparlisib.
	Consider if hospitalization is appropriate
	Pneumonitis
Please see Section 4.1.2.3.2; Table 14; 6.2.6.1.1.	and/or buparlisib Investigator Brochure Section
0	ther adverse events
Grade 1	Maintain dose level
Grade 2	Implement 50% dose reduction
Grade 3	Omit dose and discontinue study drug
Grade 4	Omit dose and discontinue
	study drug Consider if
	hospitalization if appropriate
	Other notes:
Table 10 Pesammen	
	ded dose modifications and dose delays buparlisib treatment-related toxicities
Worst toxicity CTCAE grade* (value)	During a cycle of therapy
Note: Omit dose for ≥ Grade 3 vomiting or Grade 3 nausea only if the vomiting or nausea cannot be controlled with optimal antiemetic	
All dose modifications should be based on the worst preceding toxicity.	
If the dose-limiting toxicity recurs in a patient following dose reduction, then further therapy with sonidegib will not be continued.	
If a patient requires a dose interruption of > 21 days from the intended day of the next scheduled dose because of a sonidegib-related toxicity, then the patient must be discontinued from the study.	
** Common Terminology Criteria for A	Adverse Events (CTCAE) version 4.03.

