4.1.1 Monitoring of buparlisib suspected toxicities

Patients whose treatment is interrupted or permanently discontinued due to an adverse event or clinically significant laboratory value, must be followed at least once a week for 4 weeks, and subsequently at 4-week intervals, until resolution or stabilization of the event, whichever comes first. If a patient requires a dose delay of > 21 days from the intended day of the next scheduled dose, then the patient should be discontinued from the study. If the patient requires more than 1 dose reductions, the patient should be discontinued from the study (ie, patients cannot be treated below a 50% dose reduction). All patients must be followed for adverse events and serious adverse events for 28 days following the last dose of buparlisib. All SAEs must be reported to Novartis as detailed in Section 4.3.4.2.

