4.2 Treatment Administration

4.2.1 Buparlisib Administration

The study drug buparlisib will be self-administered (by the patients themselves). The investigator will instruct the patient to take the study drug exactly as specified in the protocol. Buparlisib will be administered on a continuous once daily dosing schedule at a dose of **80mg daily**. Patients should be instructed to take the dose of buparlisib with Sonidegib (see below) daily in the morning, two hours after a light breakfast (morning meal) at approximately the same time each day. Buparlisib should be taken with a glass of water and consumed over as short a time as possible. Patients should swallow the capsules as a whole and not chew them. Do not crush capsule. Patients should continue to fast for 2 hours after the administration of each buparlisib dose.

If vomiting occurs during the course of treatment, no re-dosing of the patient is allowed before the next scheduled dose. The occurrence and frequency of any vomiting during a treatment cycle must be noted as an adverse event. If the patient forgets to take her/his dose before 6:00 PM, then the dose should be withheld that day and buparlisib should be restarted the following day.

Patients must avoid consumption of St John's Wort, Seville oranges, grapefruit or grapefruit juice, grapefruit hybrids, pummelos and exotic citrus fruits from 7 days prior to the first dose of study medication and during the entire study treatment period due to potential CYP3A4 interaction with the study medication. Patients must avoid concomitant intake of strong and moderate CYP3A4/5 inhibitors and inducers. Orange juice is allowed. All dosages prescribed and dispensed to the patient and all dose changes during the study must be recorded. If a patient requires a buparlisib dose delay of > 21 days from the previous dose, the patient must be discontinued from treatment completely and will only require a 28-day follow up visit for study completion.

Medication labels will comply with US legal requirements and be printed in English. They will supply no information about the patient. The storage conditions for study drug will be described on the medication label.

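### A toxicity delay over 21 days can end a patient's participation or not, depending on the section followed, and the observed duration of response depends on that choice

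*Combined protocol and SAP*

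**What the plan says.** Five places in the protocol give a rule for a delay of more than 21 days.

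- **Section 4.1**, for toxicity related to either drug: discontinuation is required, but "if the patient is obtaining clinical benefit (ie, SD, PR, or CR), the patient may continue treatment", at an unchanged or lower dose, once the investigator and Novartis have discussed it.
- **Closing note of Table 9**, the sonidegib table: if the interruption is "because of a sonidegib-related toxicity, then the patient must be discontinued from the study". No exception is given.
- **Closing note of Table 10**, the buparlisib table: the same sentence, still worded for sonidegib-related toxicity.
- **Section 4.1.1**, with no cause named in the sentence: "then the patient should be discontinued from the study". No exception is given.
- **Section 4.2.1**, for any buparlisib delay: "the patient must be discontinued from treatment completely and will only require a 28-day follow up visit for study completion". No exception is given.

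None of the last four refers back to Section 4.1.

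Three other places decide what happens to the data. Table 19 (footnote) runs radiological assessment to progression or the end of treatment. Section 7.1.2 uses the discontinuation date as the completion date for ongoing events, with censoring. Section 2 sets median duration of response as a secondary objective, covering time both on and after the combination.

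**The concern.** A patient who is responding or stable and has been off drug for more than 21 days because of toxicity may stay under Section 4.1 and must leave under another section. The protocol does not say which text governs. Whether that patient's response is followed to its end then turns on the page the site used, not on a planned rule. Section 4.1 also ties continued treatment to response status, which is close to the quantity the study estimates. This is a safety matter as well, because the passages give opposite instructions about re-exposure after a long toxicity hold.

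**Working it through.** The plan states no figure on this point, so the check is mainly a comparison of texts.

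**1. The rules side by side**

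| Place | Delay covered | Clock starts | Outcome | Exception |
|---|---|---|---|---|
| 4.1 | Toxicity from either drug | Not stated | Must stop | SD, PR or CR may continue after discussion |
| Table 9 note | Sonidegib-related toxicity | Day the next dose was due | Must stop | None |
| Table 10 note | Sonidegib-related toxicity | Day the next dose was due | Must stop | None |
| 4.1.1 | No cause named | Day the next dose was due | Should stop | None |
| 4.2.1 | Any buparlisib delay | Previous dose | Must stop, completely | None |

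There are three unconditional mandatory rules and one unconditional advisory rule, against one passage with a response-based exception.

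**2. Do the rules meet in the same patient?** Yes. A long hold for sonidegib-related toxicity falls under 4.1 and the Table 9 and 10 notes. A long buparlisib hold for toxicity falls under 4.1 and 4.2.1. Either way, at least one mandatory rule without exception opposes the 4.1 exception.

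**3. Does any text settle it?** The case-by-case footnote to Table 9 covers a recommended dose reduction or a recommendation to keep the dose. It does not mention the 21-day stop.

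**4. Clock start.** Both drugs are taken once daily. Put the last dose on day 0, so the next is due on day 1. More than 21 days from the previous dose is reached on day 21 + 1 = 22. More than 21 days from the due date is reached on day 1 + 21 + 1 = 23. The difference is one day.

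**5. Could the rule be triggered before the 12-week point named in Section 7.1.1?** Section 1.4.2 reports that most Grade 3/4 CK elevations on sonidegib arose 3 to 6 weeks into treatment, and that most DLTs resolved over about 4 to 8 weeks (28 to 56 days), longer than 21 days. A hold starting at week 3 passes three weeks at 3 + 3 = week 6; one starting at week 6 passes it at 6 + 3 = week 9. Both precede week 12. However, the cycle 1 DLTs in Table 1 were at 800 mg per day or more, while this trial gives 200 mg, so the frequency here is unknown.

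**6. Duration of response.** For a responder kept under 4.1, assessment continues. For one removed under 4.2.1, only a 28-day visit remains, Table 19 scanning ends with treatment, and the response is closed or censored at discontinuation. This reads the Section 7.1.2 sentence as covering response duration, because it points back to the censoring paragraph that names it.

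**7. Response rate.** The Full Analysis Set (Section 6.1) keeps every dosed patient, so the denominator does not move. A patient already in PR or CR counts as a responder under either rule. Only a patient who would first respond after the delay can change the rate. One such change is 1/12 = 0.083, or 8.3 points. With assumed counts, 5/12 = 41.7% (exact 95% CI 15.2 to 72.3) becomes 6/12 = 50.0% (21.1 to 78.9).

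**The case against.** The strongest reply is that the practical effect is small. Section 4.1 only permits continuation, and only after discussion with Novartis. Other rows of Tables 9 and 10 stop drug on their own terms, such as Grade 3 or 4 neutropenia not resolved within 7 days. The passages differ in scope: 4.2.1 does not reach a sonidegib-only delay, and the table notes are limited to sonidegib-related toxicity. The design already treats until progression, intolerable toxicity or withdrawal (Section 3.1), so an exception for patients in SD, PR or CR adds limited outcome dependence. The study is descriptive, and duration of response is secondary.

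Most of this stands as a limit on size. It rules out several stronger readings that a reader might infer:

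- *That each delay over 21 days is worth 8.3 points of response rate.* That figure belongs to one changed best-response classification, not to each delay.
- *That almost nobody stops under 4.1 and everybody stops under 4.2.1.* The permissive wording and the differing scopes do not support this.
- *That the exception covers every patient who has not progressed.* It names SD, PR or CR; a patient with no response assessment yet is not covered.
- *That the clock difference is material.* It is about one day.

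None of this removes the contradiction. Where the scopes overlap, the instructions are opposite and nothing ranks them.

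**Conclusion.** The concern holds as an internal contradiction. A patient in SD, PR or CR with a toxicity delay over 21 days can be kept or removed depending on the passage followed. The conflict itself is certain from the text; its numerical impact is not. The most direct effect is on duration of response, which may be cut off administratively although the objective extends beyond treatment. The effect on response rate is conditional: 8.3 points per cohort for each patient who would first respond after the delay, and possibly less if response is judged only at 12 weeks. The documents give no expected number of such delays, so neither the size nor the direction of the total effect can be computed. The point should be corrected, but it does not undermine the study's descriptive aim.

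**What to change.** Reconcile Section 4.1, the closing notes of Tables 9 and 10, Section 4.1.1 and Section 4.2.1 to one rule, with one scope (which drug and which causes) and one clock start. The Table 10 note needs attention in its own right, since it sits in the buparlisib table but speaks of sonidegib. Check the related three-week limits for consistency: the Grade 3/4 CK row of Table 9 and the Grade 2 and 3 rows of Table 14 (pneumonitis). Which rule to adopt is a clinical decision on which this review takes no view.

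In the report, list every patient with a delay over 21 days, showing response status at the time and whether the patient continued or stopped. The cost is one protocol clarification and one listing.
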